Appendix E – Medical History

Study Number:	PID:				
PI:	Date (mm/dd/yy): //				
To be completed by research nurs	e.				
Patient Age:					
Primary Cancer Site: Ex: oropharynx, larynx, hypophary	nx, nasopharynx, oral cavity, sinus,				
Primary Cancer Laterality (circle):					
LEFT RIGHT	BILATERAL Not Applicable/Unknown				
Clinical Stage:	T Stage:				
N Stage:	M Stage:				
Surgery for this cancer prior to rad	iotherapy:				
Medical history					
Weight (kg):	Body mass index (kg/m2):				
 □ Diabetes					
Allergies (list):					

Appendix F – Current Medications Form

Study Number:	PID:
PI:	Date (mm/dd/yy): / /

Instructions: Fill this form out at the baseline/pre-study visit. To be completed by research nurse.

Medications List

Prescription Medications:

Name of Medication	Dose	Units	Frequency	Condition Medication Taken For	Start date (mm/dd/yy)	Stop date (mm/dd/yy)	Formulation	Route	Notes
		_							

Appendix G - Compliance and Tolerability Assessment Form

Study Number:	PID:
PI:	Date (mm/dd/yy): ///
To be completed by research nurse.	
Name of Person Completing Form:	
Time Point (select one where applicable	p):
☐ Baseline (Pre-RT)	
☐ Week 1 ☐ Week 2 ☐ Week 3	☐ Week 4
☐ Week 5 ☐ Week 6 ☐ Week 7	☐ Week 8 ☐ Week 9
1-month Post-RT Follow-up	
 Number of Applications in the Last Wee May be calculated by multiplying the by 7 (Not applicable or N/A for baseline vine) 	average number of applications per day in the prior week
Number of Tubes Used in the Last Wee	k :
Did the patient discontinue application o one)	f study-assigned cream in the preceding week? (select
If yes, what was the reason for discontin	nuation of the study-assigned cream?

Appendix H - Toxicity Assessment Form

- · ·					
	r: PID:				
PI://// Date (mm/dd/yy): ///					
To be complete	ted by research nurse:				
Name of Pers	on Completing Form:				
Time Point (se	elect one where applicable):				
Baseline (F	Pre-RT)				
Week 1	☐ Week 2 ☐ Week 3 ☐ Week 4				
☐ Week 5	☐ Week 6 ☐ Week 7 ☐ Week 8 ☐ Week 9				
1-month P	ost-RT Follow-up				
To be complet	ted by research nurse and confirmed by treating radiation	oncologist:			
Radiation De	rmatitis Scale				
CTCAE Version 5.0 Grade	Definition	Present (Check one that best applies)			
0	None				
1	Faint erythema or dry desquamation				
2	Moderate to brisk erythema; patchy moist desquamation, mostly confined to skin folds and creases; moderate edema				
3	Moist Desquamation in areas other than skin folds and creases; bleeding induced by minor trauma or abrasion				
4	Life-threatening consequences; skin necrosis or ulceration of full thickness dermis; spontaneous bleeding from involved site; skin graft indicated				
5	Death				
	Oral Mucositis Scale				
CTCAE Version	Definition	Present (Check one			

5.0 Grade		that best applies)
0	None	
1	Asymptomatic or mild symptoms; intervention not indicated	
2	Moderate pain or ulcer that does not interfere with oral intake; modified diet indicated	
3	Severe pain; interfering with oral intake	
4	Life-threatening consequences; urgent intervention indicated	
5	Death	

PRO-CTCAE Symptom Assessment

To be completed by the patient.

25. PRO-CTCAE™ Symptom Term: Skin dryness						
a. In the last 7 days, what was the SEVERITY of your DRY SKIN at its WORST?						
O None O Mild O Moderate O Severe O Very severe						

28. PRO-CTCAE™ Symptom Term: Itching						
a. In the last 7 days, what was the SEVERITY of your ITCHY SKIN at its WORST?						
O None O Mild O Moderate O Severe O Very severe						

36. PRO-CTCAE™ Symptom Term: Radiation skin reaction						
a. In the last 7 days, what was the SEVERITY of your SKIN BURNS FROM RADIATION at their WORST?						
O None O Mild O Moderate O Severe O Very severe O Not applicable						

37. PRO-CTCAE™ Symptom Term: Skin darkening				
a. In the last 7 days, did you have any UNUSUAL DARKENING OF THE SKIN?				
O Yes O No				

3. PRO-CTCAE™ Symptom Term: Mouth/throat sores							
a. In the last 7 days, what was the SEVERITY of your MOUTH OR THROAT SORES at their WORST?							
O None	O None O Mild O Moderate O Severe O Very severe						
b. In the last 7 days, how much did MOUTH OR THROAT SORES INTERFERE with your usual or daily activities?							
O Not at all	O A little bit	O Somewhat	O Quite a bit	O Very much			

Appendix I – Dermatology Life Quality Index Study Number: PID: PI: Date (mm/dd/yy): ___ / ___/ ___/ To be completed by the patient. The aim of this questionnaire is to measure how much your skin problem has affected your life OVER THE LAST WEEK. Please tick (✓) one box for each question. 1. Over the last week, how itchy, sore, painful or stinging Very much has your skin been? A lot A little Not at all Over the last week, how embarrassed or self conscious Very much have you been because of your skin? A lot A little Not at all 3. Over the last week, how much has your skin interfered with Very much you going shopping or looking after your home or garden? A lot A little Not at all Not relevant 4. Over the last week, how much has your skin influenced the Very much clothes you wear? A lot A little Not at all Not relevant 5. Over the last week, how much has your skin affected any Very much social or leisure activities? A lot A little Not at all Not relevant 6. Over the last week, how much has your skin made it difficult Very much for you to do any sport? A lot A little Not at all Not relevant 7. Over the last week, has your skin prevented you from Yes working or studying? Not relevant No If "No", over the last week how much has your skin been a A lot problem at work or studying? A little Not at all Very much 8. Over the last week, how much has your skin created problems with your partner or any of your close friends or A lot relatives? A little Not at all Not relevant Over the last week, how much has your skin caused any Very much sexual difficulties? A lot A little Not at all Not relevant 10. Over the last week, how much of a problem has the Very much treatment for your skin been, for example by making your A lot A little home messy, or by taking up time? Not at all Not relevant Please check you have answered EVERY question. Thank you. To be completed by research nurse: Score:

Protocol version date 12/10/21 Page **38** of **55**

DERMATOLOGY LIFE QUALITY INDEX (DLQI) - INSTRUCTIONS FOR USE

The Dermatology Life Quality Index questionnaire is designed for use in adults, i.e. patients over the age of 16. It is self explanatory and can be simply handed to the patient who is asked to fill it in without the need for detailed explanation. It is usually completed in one or two minutes.

SCORING

The scoring of each question is as follows:

Very much	scored 3
A lot	scored 2
A little	scored 1
Not at all	scored 0
Not relevant	scored 0
Question 7, 'prevented work or studying'	scored 3

The DLQI is calculated by summing the score of each question resulting in a maximum of 30 and a minimum of 0. The higher the score, the more quality of life is impaired.

HOW TO INTERPRET MEANING OF DLQI SCORES

0 – 1 no effect at all on patient's life
2 – 5 small effect on patient's life
6 – 10 moderate effect on patient's life
11 – 20 very large effect on patient's life
21 – 30 extremely large effect on patient's life

REFERENCES

Finlay AY and Khan GK. Dermatology Life Quality Index (DLQI): a simple practical measure for routine clinical use. Clin Exp Dermatol 1994; 19:210-216.

Appendix J - Skin Care Instructions

Patient Instructions

Please apply the cream you were assigned at least twice a day, every day. Please start using the cream on the day you start radiation, and continue its use until you return for follow-up approximately 1 month after your last radiation treatment.

Other Considerations:

- Wear loose, comfortable cotton clothing in the area being treated.
- Avoid temperature extremes and use lukewarm water to wash.
- Do not use hot or ice packs, blade razor on irritated skin.
- Do not expose to the sun, rub or scratch irritated skin, patients may apply cool moist washers
 if skin feels itchy or hot.
- Pat skin dry with a soft towel after washing or air dry.
- Do not use any tapes, band aids, or dressing unless advised by clinicians.
- Do not use other topical preparations in the treatment area.
- Rinse off immediately in fresh water if swimming in a pool or salt water (if the skin is intact)

Skin Care during Radiation Therapy

ALL MOISTURIZERS MUST BE APPROVED BY YOUR NURSE:

Protocol version date 12/10/21

Page **40** of **55**

Apply moisturizer at least twice daily. Start using within the first week of your radiation therapy.

*IMPORTANT: Do not apply the moisturizer within four hours before your daily radiation treatment appointment.

Examples of good moisturizers that do not interfere with the radiation:

- Aveeno Skin Relief lotion, fragrance-free
- Eucerin
- Lubriderm
- · Calendula cream or gel
- Aloe Vera gels
- Cetaphil
- CeraVe
- Petroleum based with mineral oil ointments: Aquaphor, Balmex, Elta

Soaps:

Use a gentle soap for bathing/showering such as Dove or Cetaphil.

Deodorants:

You may use regular strength deodorant/anti-perspirant such as:

Dove

Secret

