6.2 Treatment Administration

Beginning on the first day of RT, patients will be instructed to apply skin care according to their randomization arm (Section 6.2.1). The patient will be instructed to apply the assigned agent every day as needed, but at least twice daily, to the skin of the head and neck within the region of interest.

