6.2.3 Routine Skin Care

Routine skin care will include various standard-of-care, commercially available agents. A list of example agents will be provided to patients in this arm (Appendix J).

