7.1.2 Weekly Visits During RT

During regular visits with medical staff, study subjects will also meet with study staff. Study staff will obtain photographs of the area of irradiation. Study staff will obtain photographs of the area of irradiation. Study personnel will collect the skin toxicity assessment (Appendix H). Any adverse events will be noted and addressed. Subjects will complete the Dermatology Life Quality Index (Appendix I). Study personnel will provide KeraStat Cream, as needed, to subjects randomized to receive KeraStat Cream. Subjects randomized to standard of care will follow the instructions of their radiation oncologist.

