11.0 Statistical Considerations

11.1 Analysis of Primary Objective

The completion rate will be used as a measure of feasibility, with participants with an average of 10 or more applications per week being classified as compliant. In each arm, a 95% confidence interval will be calculated around the estimate of compliance.

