11.2 Analysis of Secondary Objective

- 11.2.1 The rate of discontinuation for any reason will be used as a measure of tolerability, with patients who do not discontinue the skin care regimen being classified as tolerant. In each arm, a 95% confidence interval will be calculated around the estimate of tolerability.
- 11.2.2 Proportion of EASR (CTCAE v5.0 Grade 2+ radiation dermatitis) will be compared between the KeraStat group and the RSC group at the end of treatment, using a Fisher's exact test.
- 11.2.3 Mean scores of the modified PRO-CTCAE patient-reported outcome scales collected each week over the 6-7 weeks of radiation therapy and at the onemonth post treatment follow-up visit will be compared between the KeraStat and RSC groups using a simple repeated measures analysis of variance model with treatment group as the independent variable of interest.
- 11.2.4 Mean DLQI score at each time point will be compared between the KeraStat and RSC groups, again using a simple repeated measures analysis of variance model with treatment group as the key independent variable. Additionally, the mean of the highest DLQI score across all time points will be compared between the KeraStat and RSC groups using a t-test.
- 11.2.5 Skin coverage (calculated as number of tubes of KeraStat Cream used per week) will be summarized with a frequency distribution and computation of central tendency and variability (mean, median, and standard deviation).

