11.3 Power and Sample Size

Up to 28 subjects will be enrolled on this pilot study to assure retention of at least 24 complete, evaluable subjects for the primary endpoint. The expected accrual rate is four per month with accrual lasting approximately six months. Participants will be randomized equally (n=12 per group) to standard of care or KeraStat Cream. With 12 participants in each treatment group expected to complete the study, we will be able to calculate a 95% confidence interval around the compliance rate in each group with a

maximum total confidence interval width of 0.578 (this maximum occurs if the compliance proportion is 0.5).

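### Appendix J's moisturizer part lets skin care start within the first week of RT, while section 6.2 and the leaflet's own opening say the first day; the consequence is minor

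*Combined protocol and SAP*

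**What the plan says.** Section 6.2 sets one start for both arms: "Beginning on the first day of RT, patients will be instructed to apply skin care according to their randomization arm". Appendix J, the patient leaflet, opens in the same sense: "Please start using the cream on the day you start radiation".

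Further down the leaflet, under a general heading on skin care during RT and shortly before the list of example moisturizers, it says: "Start using within the first week of your radiation therapy".

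Two other sections bear on who reads that line:

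- Section 6.2.3, on RSC: "A list of example agents will be provided to patients in this arm (Appendix J").
- Section 7.1.2: "Subjects randomized to standard of care will follow the instructions of their radiation oncologist". It names no start day.

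The analyses that use early data are these:

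- Section 11.1 applies one compliance rule in both arms, with "participants with an average of 10 or more applications per week being classified as compliant".
- Section 11.2.3 compares mean PRO-CTCAE scores "collected each week over the 6-7 weeks of radiation therapy" and at the one-month visit.
- Section 11.2.4 compares mean DLQI scores over the time points, and each patient's highest DLQI score.
- Section 11.3 gives the size: "Participants will be randomized equally (n=12 per group) to standard of care or KeraStat Cream".

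**The concern.** The patient acts on the leaflet, and the leaflet gives two start times. The looser one sits with the moisturizer list, so an RSC patient is the likelier reader to take it as applying to them. The opening speaks of an assigned cream, whereas RSC patients choose a commercial product. The opening also tells patients to use no other topical product in the treated area, so a KeraStat patient has little reason to act on the moisturizer list.

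If some RSC patients take up the allowance, the arms differ in exposure early in RT for a reason unrelated to the cream. Their Week 1 application counts fall, and with them the average used in section 11.1. The Week 1 symptom and quality-of-life scores would then set KeraStat users beside some RSC patients who had used little or nothing. As reproduced, Appendix G counts applications in the past week but shows no start date. A low Week 1 count would be visible, but a late start taken at the leaflet's word could not be told apart from missed applications.

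**Working it through.** **1. Which start days satisfy which text**

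| Start day | Section 6.2 | Appendix J, opening | Appendix J, moisturizer part |
|---|---|---|---|
| Day 1 | yes | yes | yes |
| Days 2 to 7 | no | no | yes |

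The late start is therefore allowed by one line and ruled out by two others.

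**2. Size of the gap**

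- Calendar week: 7 − 1 = 6 days, which is 6/49 = 12.2% to 6/42 = 14.3% of a 7- or 6-week RT course.
- Monday-to-Friday treatment week beginning on a Monday: 5 − 1 = 4 days, which is 4/49 = 8.2% to 4/42 = 9.5%.

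**3. The plan's own figure**

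For 6 of 12 compliant, the exact (Clopper-Pearson) 95% interval is 0.211 to 0.789, a width of 0.578. This matches section 11.3. The start-day conflict does not alter it.

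**4. A twice-daily user**

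Inputs: at least 2 applications per day (section 6.2); RT of 6 to 7 weeks plus 4 weeks of follow-up (section 11.5). Section 11.1 does not state the averaging window, so n = 6, 7, 10 and 11 weeks are all shown. With start day d, Week 1 holds 2 × (8 − d) applications. For d = 7 that is 2 instead of 14:

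- n = 6: (2 + 5 × 14)/6 = 72/6 = 12.0
- n = 7: (2 + 6 × 14)/7 = 86/7 = 12.3
- n = 10: (2 + 9 × 14)/10 = 128/10 = 12.8
- n = 11: (2 + 10 × 14)/11 = 142/11 = 12.9

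All are above 10, so this patient stays compliant.

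**5. Patients near the cut-off**

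The answer depends on what is assumed about Week 1.

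*Assumption A: 2 per day in Week 1 from the start day, then a different weekly rate r.* The rate needed to average 10 is r = (10n − 2(8 − d))/(n − 1).

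| Start day | Week 1 count | r, n = 6 | r, n = 7 | r, n = 10 | r, n = 11 |
|---|---|---|---|---|---|
| 3 | 10 | 10.0 | 10.0 | 10.0 | 10.0 |
| 4 | 8 | 10.4 | 10.3 | 10.2 | 10.2 |
| 5 | 6 | 10.8 | 10.7 | 10.4 | 10.4 |
| 6 | 4 | 11.2 | 11.0 | 10.7 | 10.6 |
| 7 | 2 | 11.6 | 11.3 | 10.9 | 10.8 |

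*Assumption B: one constant rate from the start day.* A patient who is k days late needs 70n/(7n − k) per week.

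- k = 6: 420/36 = 11.7 (n = 6) down to 770/71 = 10.8 (n = 11).
- k = 4: 420/38 = 11.1 (n = 6) down to 770/73 = 10.5 (n = 11).
- k = 1: a patient at exactly 10 per week averages (10/7 × 41)/6 = 9.76 over 6 weeks, so even a day-2 start can matter for someone exactly on the line.

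Under both assumptions the patients at risk lie between 10 and about 11.7 per week.

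**6. One reclassified RSC patient**

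1/12 = 8.3 percentage points. For example, 10/12 = 83.3% (exact 95% CI 51.6 to 97.9%) becomes 9/12 = 75.0% (42.8 to 94.5%). The first interval is 97.9 − 51.6 = 46.3 points wide, so the shift is well inside the uncertainty already accepted. The documents do not say how many patients, if any, would start late.

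**7. Skin outcomes**

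No effect size can be derived from the documents. Section 11.2.3 puts all weekly scores and the one-month score into one repeated-measures model with treatment group as the variable of interest. Week 1 is thus one of 6 + 1 = 7 to 7 + 1 = 8 assessments from the start of RT. Section 11.2.4 refers to DLQI at each time point, within the same kind of model. The Grade 2+ dermatitis test in section 11.2.2 is made at the end of treatment.

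**The case against.** The strongest reply is that the start day is already fixed. Section 6.2 and the first paragraph of the leaflet bind RSC patients as much as KeraStat patients. The later line sits among general advice on soaps and deodorants, and a day-1 start meets every text. Section 6.2.3 sends RSC patients a list of agents; it does not say that the timing sentence is for them alone. If both arms follow the whole leaflet in the same way, the arms need not differ. All of this stands, and it is why the gap between arms is a possibility and not a feature of the design. It does not remove the contradiction, because a patient who reads the moisturizer part has written permission to start later than the protocol intends.

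It is also fair to say that Week 1 is not a sharply defined exposure point. Assessments may fall 5 days either side of the weekly visit (section 7.2), and Appendix G asks about the past week, so Week 1 counts may be incomplete even for patients who start on day 1. RSC is deliberately loose in other respects too. Both points reduce the weight of the concern.

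A reader might infer that the protocol builds a 6-day delay into the control arm, or that the comparison of skin outcomes is biased in favour of KeraStat. The documents support neither inference. The delay is allowed by one unlabelled line and contradicted by two others. No separate Week 1 contrast is specified in section 11.2.3, and there is no information on late starters or on what a few days without moisturizer would do to the skin.

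**Conclusion.** The contradiction is real and in the current text. Its severity is minor. On the reading that section 6.2.3 suggests, an RSC patient could start up to 6 calendar days late (4 on a Monday-to-Friday reading), with somewhat lower early exposure and a lower Week 1 count. The weekly PRO-CTCAE and DLQI comparisons could be slightly affected, to an extent that the documents do not allow to be estimated.

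For compliance, only RSC patients a little above 10 applications per week could change class. A patient who keeps to the twice-daily instruction does not. The KeraStat estimate, which answers the primary objective, is unaffected as long as the moisturizer part is read as RSC text. If KeraStat patients followed that line too, the gap between arms would disappear and the conflict with section 6.2 would remain.

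These conclusions assume a 7-day week for the 6-day figure, averaging windows of 6 to 11 weeks, and the two Week 1 patterns shown in the working.

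**What to change.** In the moisturizer part of Appendix J, replace "Start using within the first week of your radiation therapy" with *Start on the day you start radiation*. This matches section 6.2 and the leaflet's opening and closes the allowance whichever arm reads it. The cost is one phrase in a patient leaflet, with no extra visits, forms or data and no change to the analysis or the sample size.

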Appendix K – Mandatory STRC SAE Reporting Guidelines

Data and Safety Monitoring	Date: 02/11/2021
Committee (DSMC) Serious Adverse	
Event (SAE) Notification SOP	

Mandatory DSMC SAE Reporting Requirements in WISER

This document describes reporting requirements of adverse events from WFBCCCInvestigator Initiated interventional trials to the Data and Safety Monitoring Committee (DSMC). A trial is considered a WFBCCC Investigator Initiated interventional trial if the following criteria are met:

- 1) The Principal Investigator (PI) of the trial is a member of a department at the Wake Forest University Baptist Medical Center.
- 2) WFBCCC is considered as the primary contributor to the design, implementation and/or monitoring of the trial.
- 3) The trial is designated as "Interventional" using the Clinical Research Categories definitions provided by the NCI in the Data Table 4 documentation. (https://cancercenters.cancer.gov/GrantsFunding/DataGuide#dt4)

There are two distinct types of WFBCCC Investigator Initiated interventional trials based on where patient enrollment occurs. These include:

- Local WFBCCC Investigator Initiated interventional trials defined as trials where all patients are
 enrolled from one of the WFBCCC sites. These include the main outpatient Cancer Center
 clinics (located in Winston-Salem) as well as WFBCCC affiliate sites located in Bermuda Run
 (Davie Medical Center), Clemmons, Lexington, High Point, or Wilkesboro.
 - 2) Multi-Center WFBCCC Investigator Initiated interventional trials defined as trials where patients are enrolled from other sites in addition to WFBCCC sites.

There are three types of trials that are included in this category:

- a. Trials sponsored by the NCI Community Oncology Research Program (NCORP) that are conducted at multiple sites where the PI is a member of a department at the Wake Forest University Baptist Medical Center.
- b. Trials sponsored by Industry that are conducted at multiple sites and the PI is a member of a department at the Wake Forest University Baptist Medical Center.
- c. Trials sponsored by WFBCCC that are conducted at multiple sites and the PI is a member of a department at the Wake Forest University Baptist Medical Center.

All Adverse Events (AEs) and Serious Adverse Events (SAEs) that occur on any patients enrolled on WFBCCC Investigator Initiated Interventional trials must be entered into the WISER system. The only exception to this requirement is for patients enrolled on NCORP trials at non- WFBCCC sites. AEs and SAEs for NCORP patients enrolled at WFBCCC sites must be entered into the WISER system. Once these AEs and SAEs are entered in WISER, certain actions must be taken regarding the reporting of specific Adverse Events to the DSMC.

All Adverse Events that occur during protocol intervention (defined below) and are coded as either 1) unexpected grade 4, 2) unplanned inpatient hospitalization > 24 hours (regardless of grade), or grade 5 (death) must be reported to the DSMC using the using the SAE console in WISER.

A research nurse or clinical research coordinator when made aware that an adverse event meets one of the above criteria has occurred on a WFBCCC Investigator Initiated interventional trial, is responsible for informing a clinical member of the DSMC by phone (or in-person) about the adverse event. The nurse/coordinator should contact the treating physician prior to calling the DSMC clinical member to obtain all details of the SAE, as well as all associated toxicities to be recorded along with the SAE. In addition, this nurse or coordinator is responsible for entering the adverse event information into the SAE console in WISER. Once the adverse event has been entered into the SAE console an email informing the entire DSMC will be generated.

THESE REPORTING REQUIREMENTS APPLY TO any staff member on the study team for a WFBCCC Institutional Interventional trial. Ultimately, the protocol PI has the primary responsibility for AE identification, documentation, grading and assignment of attribution to the investigational agent/intervention. However, when an AE event as described above is observed, it is the responsibility of the person who observed the event to be sure that it is reported to the DSMC.

What is considered during protocol intervention?

During protocol intervention is considered to be the time period while a patient is on study treatment or during the time period within 30 days of last study treatment (even if patient begins a new (non-study) treatment during the 30 days). This window of 30 days should be the standard window to be used in all protocols unless a specific scientific rationale is presented to suggest that a shorter window can be used to identify events. If it is a trial sponsored by Industry and the sponsor requires a longer window for monitoring of SAEs, then the longer window of time specified by the sponsor should be followed.

What is considered as an Unexpected Grade 4 event?

Any grade 4 event that was not specifically listed as an expected adverse event in the protocol should be considered as unexpected. A grade 4 adverse event can be considered to be unexpected if it is an event that would not be expected based on the treatment being received or if it is unexpected based on the health of the patient. In either case, if there is any uncertainty about whether a grade 4 adverse event is expected or unexpected it should be reported to DSMC.

DSMC notification responsibilities of the person (e.g., nurse) handling the reporting/documenting of the SAE in WISER:

- 1. Make a phone call (or speak in person) to the appropriate clinical member of the DSMC according to the schedule as listed below (page if necessary).
- 2. Enter a new SAE into the SAE module that is located in the Subject>> CRA Console inWISER WITHIN 24 HOURS of first knowledge of the event. Information can be entered and saved, but the DSMC members will not be notified until a date is entered into the DSMC Notification Date Field. This will ensure that all persons that need to be made aware of the event (i.e., PI, study team members and DSMC members) will be notified; remember to file a copy of the

confirmation.

- Document that the appropriate person(s) on the DSMC has been contacted. Indicate the name of the DSMC clinician that was contacted and the date and time contacted in the Event Narrative field in the SAE console of the particular subject.
- 4. Document whether or not the protocol should be suspended based on the discussion with the DSMC clinician. This is the major function of the email notification. Enter whether the protocol should be suspended in the Event Narrative Field.
- 5. Follow up/update the clinical member(s) of DSMC regarding any new developments or information obtained during the course of the SAE investigation and reporting process.

Elements needed to complete the SAE form in the Subject Console in WISER (see Screen Shot 3):

- 1. Event Date
- 2. Reported Date
- 3. Reported by
- 4. If Grade 5, enter Death Date
- 5. If Grade 5, enter Death occurred: within 30 days
- 6. Event Narrative: Brief description (include brief clinical history relevant to this event, including therapies believed related to event). Begin narrative with the DSMC clinician who was notified and Date/Time notified. In addition, state attribution by DSMC clinician as either "Unrelated", "Unlikely", "Possibly", "Probably", or "Definitely". Always include the following here:
 - i. DSMC clinician name, date/time contacted and comments
 - ii. Date of last dose before the event
 - iii. Is suspension of the protocol needed? Y/N
- 7. Treating Physician comments
- 8. PI comments, if available
- 9. Protocol Attribution after discussion with DSMC clinician
- Outcome (Fatal/Died, Intervention for AE Continues, Migrated AE, Not Recovered/Not Resolved, Recovered/Resolved with Sequelae, Recovered/Resolved without Sequelae, Recovering and Resolving)
- 11. Consent form Change Required? Y/N
- 12. SAE Classification *This is required in order for the email notification to be sent*
- 13. Adverse Event Details Enter all details for each AE associated with the SAE.
 - a. Course start date
 - b. Category
 - c. AE Detail
 - d. Comments
 - e. Grade/Severity
 - f. Unexpected Y/N
 - g. DLT Y/N
 - h. Attributions
 - i. Action
 - j. Therapy
 - k. Click ADD to attach the AE Detail to the SAE.
- 14. Enter Date Notified DSMC -- *This is required for the email notification to be sent*
- 15. Click Submit. The auto-generated notification email will disseminate within 5 minutes. If you do Protocol version date 12/10/21 Page **44** of **55**

